8.2.2 Elimination constant rate and terminal elimination half-life

To determine the terminal elimination half-life of dapivirine from blood, we will use the dapivirine concentrations from samples at 24 h, 48 h and 72 h after the time of dosing. To determine the terminal elimination half-life of dapivirine from rectal fluid and rectal tissue, for each participant we will use their concentration at 120 min after dosing and their concentration at either 24 h, 48 h or 72 h after dosing. Given the sampling schedule, only about half of the participants will have concentrations of rectal fluid and rectal tissue at two of these sampling time points available.

For the calculation of the terminal elimination half-life, for each participant, we will assume a mono-compartmental model, with the concentration at time t given by:

$$C(t) = a e^{-\beta t}$$

To estimate each participant's elimination rate constant (β), we will use linear regression on the log-transformed concentrations of dapivirine, with time (of sampling) as predictor, along with an indicator for samples obtained after multiple dosing. The resulting absolute value of the slope will correspond to the elimination rate constant β . The terminal elimination half-life for each participant will be calculated from the elimination rate constant as

$$t_{1/2} = \frac{\log(2)}{\beta}$$

We will summarize terminal elimination half-life ($t_{1/2}$) for blood, rectal fluid and rectal tissue, using descriptive statistics and will provide a 95% confidence interval, using a Student's-t distribution approximation.

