2.3.1 Randomization

Participants were randomized in a 2:1 ratio to the dapivirine and placebo arms, stratified by study site.

Participants were also sequentially assigned in a 1:1 ratio to provide intensive PK samples at either 30-60 or 120 minutes after administration of the gel on Visits 3 and 13. Participants were also sequentially assigned in a 1:1:1 ratio to provide intensive PK samples at either Visits 4 and 14, Visits 5 and 15 or Visits 6 and 16.

The randomization scheme has been generated and maintained by the MTN SDMC.

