2.3.3 Sample Size and Power

The proposed sample size for this study was 27 participants, with 18 in the active arm and 9 in the control arm. The study has power to detect only very large differences in safety event rates between active and control arms. With 5% significance level, the study has 85% power to detect a rate in safety endpoint greater than 67% in the active arm when assuming an 11.2% rate in the control arm. On the other hand, the proposed sample size ensures a reasonable frequency of safety events that are not too rare. For example, if the true event rate of an adverse event is 10%, then the probability of observing at least one adverse event in the study is 85%.

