3. GENERAL DATA ANALYSIS CONSIDERATIONS

3.1 Analysis Set(s)

The analysis set for the primary safety endpoint will include all enrolled participants who received at least one dose of the study product (either the dapivirine or the placebo gel). The analysis set for the primary PK endpoint will include enrolled participants who were assigned to receive the active treatment and who received at least one dose of the study product (dapivirine gel).

Participants enrolled but lost to follow-up between enrollment visit (Visit 2) and the first dosing visit (Visit 3) or who were never administered the gel will not be included in the analysis sets. Enrolled participants who received the study product but were found to be ineligible (enrollment violations) will preferably be included in the analysis sets, in order to capture all adverse events potentially related to the study product. Sensitivity analysis of the primary safety endpoint excluding these participants will be conducted.

All the participants to be excluded from the analysis sets will be identified prior to data lock and to the unblinding of the data and the reasons for exclusion will be properly documented.

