8.2 Pharmacokinetics Evaluations

8.2.1 Dapivirine concentrations in blood, rectal fluid and rectal tissue

For participants in the active arm only, we will report the dapivirine concentration in blood at all time points where a sample was obtained. At each sampling time point, the concentration of dapivirine will be summarized using descriptive statistics (mean, standard deviation, median, interquartile range and range, along with number of participants). Also, 95% confidence intervals for the mean concentration will be obtained, using a Student's-t distribution approximation. Given the small number of samples that are expected for some sampling points, a log transformation of the concentrations will be considered if the data suggest strong skewness. No formal statistical testing will be performed.

For concentrations of dapivirine that fall below the corresponding assay's lower limit of quantification (LLOQ), we will use a value equivalent to half the LLOQ of the assay. The number and percentage of samples that fall below the LLOQ for any given sampling time point will be reported.

The time-points in the proposed sampling schedule were selected to roughly provide a description of some important PK characteristics. The sample taken 30-60 min after dosing time will be used to describe the concentrations soon after a gel dose. The sample taken 2 h after dosing will be used to roughly approximate peak concentrations. Concentrations from 2 h, 24h, 48 h and 72 h after dosing will be used to estimate terminal elimination half-life. The sample taken at dosing time after multiple doses will be used to estimate the concentration accumulation with multiple dosing (approach to steady state).

The following figures and tables are planned to describe the concentration of dapivirine in blood, rectal fluid and rectal tissue:

Dapivirine concentrations in blood

- Table summarizing the concentration of dapivirine after single dose: at time of dosing (visit 3), 30-60 min (visit 3), 120 min (visit 3), 24 h (visit 4), 48 h (visit 5) and 72 h (visit 6) after the time of dosing.
- Table summarizing the concentration of dapivirine after the first of multiple doses: at time of dosing (visit 7) and 24 h after time of dosing (visit 8).
- Table summarizing the concentration of dapivirine after multiple doses: at time of dosing (visit 13), 30 – 60 min (visit 13), 120 min (visit 13), 24 h (visit 14), 48 h (visit 15) and 72 h (visit 16) after time of dosing.

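### The SAP conflicts on whether the 2 h sample enters the blood half-life, and it labels a rectal slope drawn from that sample 'terminal' on an assumption the sampling cannot check

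*SAP*

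**What the plan says.** Section 8.2.1 of the SAP gives the 2 h sample two roles. First, "The sample taken 2 h after dosing will be used to roughly approximate peak concentrations". Then, with no matrix named, "Concentrations from 2 h, 24h, 48 h and 72 h after dosing will be used to estimate terminal elimination half-life".

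Section 8.2.2 sets different rules by matrix. For the half-life "from blood, we will use the dapivirine concentrations from samples at 24 h, 48 h and 72 h after the time of dosing"; the 2 h sample is not listed. For the two rectal matrices the rule is that "for each participant we will use their concentration at 120 min after dosing and their concentration at either 24 h"; depending on the assigned visit, the later sample may instead be the one at 48 or 72 h.

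The same section assumes a mono-compartmental model. It regresses log concentration on time within each participant, with an indicator for the multiple-dose period, and converts the slope to a half-life. The individual half-lives in all three matrices are then summarized under one name, terminal elimination half-life, with a Student's t interval. The plan acknowledges that "only about half of the participants will have concentrations of rectal fluid and rectal tissue at two of these sampling time points available".

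**The concern.** There are two separate problems.

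**Blood.** Sections 8.2.1 and 8.2.2 disagree on whether the 2 h concentration enters the fit. Two analysts following different sections would report different blood half-lives, and nothing says which section governs.

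**Rectal fluid and tissue.** The slope starts at a sample the plan itself associates with peak. If concentrations fall quickly at first and slowly later, a line from 2 h to one late sample mixes the two phases and gives too short a half-life. The amount of mixing depends on whether the late sample was assigned to 24, 48 or 72 h, so the summary pools three different quantities.

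Rectal fluid and tissue are two of the three matrices in the primary PK endpoint (section 2.2). A rectal value that is too short, tabulated beside a 24-72 h blood value under the same name, would invite a comparison between compartments that the data do not support.

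**Working it through.** **1. The plan's own figure.** Section 2.3.3: "The proposed sample size for this study was 27 participants, with 18 in the active arm and 9 in the control arm". Section 3.1 limits the PK set to the active arm. Section 2.3.1 has participants "sequentially assigned in a 1:1 ratio to provide intensive PK samples at either 30-60 or 120 minutes after administration of the gel", and separately assigns each one, 1:1:1, to a single late sampling time.
- With a 2 h rectal sample: 18 × 1/2 = 9. The stated share of about half reproduces.
- Per late time among those: 9 × 1/3 = 3.

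**2. What one participant's data can show.** A contributor has times 2 h and T (24, 48 or 72 h) in each of two dosing periods, so up to four observations. The regression has three parameters (intercept, time, multiple-dose indicator), leaving 4 − 3 = 1 residual degree of freedom. At nominal times the fitted slope is the mean of the two period slopes. The one residual degree of freedom measures how far those two slopes differ. With only two distinct times, curvature cannot be examined.

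**3. The estimator.** For late time T,

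t½ = ln 2 × (T − 2) / [ln C(2) − ln C(T)].

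**4. Under the plan's model.** If C(t) = a·exp(−βt), the denominator is β(T − 2) and t½ = ln 2 / β for every T. A true 24 h returns 24, 24 and 24 h. There is no bias.

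**5. If there is a faster early phase.** The SAP gives no decay parameters, so these profiles are assumptions. Both have a true terminal half-life of 24 h.

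- *Profile A:* half of the 2 h level decays with a 2 h half-life. Scale C(2) = 1. Then C(24) = 0.5·2^(−11) + 0.5·2^(−22/24) = 0.265, and t½ = 0.693 × 22 / 1.328 = 11.5 h.
- *Profile B:* 90% of the amount at time 0 decays with a 4 h half-life. C(2) = 0.9 × 0.707 + 0.1 × 0.944 = 0.731; C(24) = 0.9·2^(−6) + 0.1 × 0.5 = 0.0641. Then t½ = 0.693 × 22 / 2.434 = 6.3 h.

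| Assumed profile | T = 24 h | T = 48 h | T = 72 h | Fit to 24, 48, 72 h |
|---|---|---|---|---|
| Mono-exponential | 24.0 | 24.0 | 24.0 | 24.0 |
| A | 11.5 | 15.8 | 17.9 | 24.0 |
| B | 6.3 | 9.5 | 11.9 | 20.4 |

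In A and B the two-point value is too short and rises with the assigned late time. The 24-72 h fit is closer, though in B it also falls short of 24 h.

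**6. What a late-sample rectal fit could deliver.** Each participant has one late rectal time, so no individual 24-72 h slope exists; only a fit pooled across participants is possible. With 18/3 = 6 participants per time, the sum of squares of time is 6 × (24² + 0² + 24²) = 6,912. Assume log-scale SDs of 0.7 between and 0.5 within participants, and two periods each:

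SE = √[(0.49 + 0.25/2) / 6,912] = √(0.615 / 6,912) = 0.0094 per hour.

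- At a true 24 h the slope is 0.693/24 = 0.0289. The 95% limits (±1.96 SE) are 0.0104 and 0.0474, so the half-life runs from about 15 to 67 h. With t on 16 degrees of freedom it is about 14 to 78 h.
- The expected lower slope limit reaches zero when ln 2 / t½ equals the margin. That is a true half-life of about 38 h with the normal quantile and about 35 h with t. Beyond it the half-life has no finite upper limit.

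**The case against.** The strongest defence is that section 8.2.2 states its model, and under that model the two-point rule is exact at every schedule. Nothing in the SAP shows a fast early phase; calling 2 h roughly peak raises doubt but does not establish one. The sizes for profiles A and B come from assumed inputs. All of this stands, and it is why the point is conditional. It does not remove the difficulty that the assumption cannot be checked within a participant, or that the plan leaves out the 2 h sample for blood while using it for the rectal matrices under the same label.

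A reader might infer stronger points, which the SAP does not support:

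- **That the rectal rule contradicts section 8.2.1.** It does not: both use 2 h. The textual conflict concerns blood. A different rule for another matrix is not in itself a contradiction, and the split rectal sampling gives a reason for one.
- **That using about half the arm invalidates the estimate.** The plan discloses this and it follows from the sampling assignment. It costs precision (t-interval half-width of 0.77 SD at n = 9, against 0.50 SD at n = 18) but does not change what is estimated. The other participants' concentrations are still tabulated and plotted.
- **That a pooled 24-72 h model must replace the rule.** Step 6 of the working shows the price: decay is then estimated only between participants, and the interval may be unbounded. Exchanging possible bias for that much imprecision is a matter of judgement.

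**Conclusion.** The point holds in a limited form. The conflict over the 2 h sample for blood is plain in the text and needs no assumption. For rectal fluid and tissue, the quantity equals the terminal half-life only if decline is mono-exponential from 2 h, and the sampling scheme cannot test that. It would go too far to say that the rule fails to estimate a terminal half-life at all, since under the stated model it succeeds.

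For an assumed true value of 24 h, the consequence ranges from no bias, through 11.5 to 17.9 h by schedule (profile A), to 6.3 to 11.9 h (profile B). The direction and the dependence on assigned visit hold for any profile with a faster early phase; the size rests on the assumed one.

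This should be fixed but is not critical. The primary PK endpoint is the concentrations, which the half-life rule does not touch, and half-life is a derived descriptive summary with no test attached.

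**What to change.** - **Blood:** amend section 8.2.1 so that the half-life uses 24, 48 and 72 h, as in section 8.2.2.
- **Rectal fluid and tissue:** rename the quantity *apparent half-life from 2 h*, report it separately for the 24, 48 and 72 h schedules, and state that it is not comparable with the blood terminal half-life.
- **Supplementary analysis:** for each rectal matrix, fit a pooled log-linear mixed model to the 24, 48 and 72 h samples of all active participants, with a random participant intercept, time since dose and the multiple-dose indicator. Report the slope with its confidence interval, and note that it is estimated between participants and may give no finite upper limit for the half-life.

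The cost is revised SAP wording and one extra model per rectal matrix; no new data are needed. The drawbacks are a less favourable label, about 3 participants per schedule in the descriptive table, and a wide interval from the supplementary model.

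### The half-life rule uses the absolute slope and so hides non-declining profiles, and its t-interval on an untransformed reciprocal can distort the mean half-life, usually upward

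*SAP*

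**What the plan says.** SAP section 8.2.2 describes the half-life calculation in four steps.

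- **Model:** "for each participant, we will assume a mono-compartmental model, with the concentration at time t given by" C(t) = a·exp(−βt).
- **Fit:** "we will use linear regression on the log-transformed concentrations of dapivirine, with time (of sampling) as predictor", plus an indicator for samples taken after multiple dosing. Each participant therefore has one slope common to both dosing periods and two intercepts.
- **Rate constant:** "The resulting absolute value of the slope will correspond to the elimination rate constant" β, and the half-life is log(2)/β.
- **Summary:** half-life is summarised "using descriptive statistics and will provide a 95% confidence interval" based on Student's t.

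For blood, "we will use the dapivirine concentrations from samples at 24 h, 48 h and 72 h after the time of dosing". For rectal fluid and tissue, each participant contributes "their concentration at 120 min after dosing and their concentration at either 24 h, 48 h or 72 h after dosing", and "only about half of the participants will have concentrations of rectal fluid and rectal tissue at two of these sampling time points available".

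Three other provisions matter. Section 5 defines the descriptive statistics for continuous outcomes to include median, quartiles and range as well as mean and SD. Section 8.2.1 allows a log transformation, but for concentrations only. It also replaces values below the quantification limit (LLOQ) by half that limit.

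**The concern.** On the log scale the model has slope −β, so β = −slope. The absolute value gives the same number only when the fitted slope is negative, and the SAP neither requires nor checks that. A participant whose fitted concentrations do not decline has no estimable elimination half-life from these data. Under the written rule that participant still enters the table with an ordinary-looking positive value.

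The second issue is scale. A half-life is a reciprocal of the slope, and it grows without bound as the slope nears zero. An arithmetic mean and t-interval on that scale give most influence to the participants whose slopes are least well determined. The mean half-life and its interval, reported under the primary pharmacokinetic objective, could then say more about a few flat profiles than about dapivirine elimination.

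**Working it through.** The SAP states no half-life, variability or precision figure, so there is no planned figure to reproduce.

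**Inputs from the SAP.** The sample size is "27 participants, with 18 in the active arm and 9 in the control arm", so up to 18 participants have blood slopes and about 9 have rectal slopes. Section 8.2.1 also names the 2 h sample for half-life. I follow 8.2.2, which uses 24, 48 and 72 h for blood.

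**Inputs assumed.** Residual SD σ on the log scale, and the true half-life. Neither is in the SAP, so a range is shown.

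**Precision of the slope.**
- Blood: 6 points, 3 parameters, 3 residual degrees of freedom. The sum of squares of time is 2 × (24² + 0 + 24²) = 2304, so SE(slope) = σ/√2304 = σ/48.
- Rectal: 4 points, 3 parameters, 1 residual degree of freedom. With spacing d, the sum of squares is 2 × d²/2 = d², so SE(slope) = σ/d with d = 22, 46 or 70 h.

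**The sign rule.** This needs no assumption. Slopes of −0.0093/h and +0.0093/h both give log(2)/0.0093, about 75 h. A nearly flat rise of +0.00032/h gives more than 2,000 h. If every value is at half the LLOQ, the slope is 0 and the half-life is undefined.

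**Chance of a positive blood slope.** With true half-life H and normal error, this is Φ(−(log(2)/H)/(σ/48)). At σ = 0.5:
- H = 48 h: Φ(−0.693/0.5) = Φ(−1.39) = 8.3%. At least one among 18: 1 − 0.917^18 = 79%.
- H = 24 h: Φ(−2.77) = 0.3%. At least one among 18: about 5%.
- H = 12 h: Φ(−5.55), effectively zero.

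**Effect on the reported mean.** I simulated slopes with these standard errors, all participants sharing one true half-life, σ = 0.5. Typical means the median over simulated trials.

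| Sample | True half-life | Typical reported mean | t-interval lower limit below zero |
|---|---|---|---|
| Blood, n = 18 | 12 h | 12.4 h | about 0% |
| Blood, n = 18 | 24 h | 28 h | about 4% |
| Blood, n = 18 | 48 h | 98 h | about 25% |
| Rectal, n = 9 | 24 h | 30 h | about 17% |

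For blood at 48 h, σ = 0.3 gives a typical mean of 64 h.

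**Wider range for blood.** Here the half-life varies between participants with an assumed CV of 30%. Entries are the typical reported mean divided by the true mean.

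| Median half-life | σ = 0.2 | σ = 0.5 | σ = 0.8 | σ = 1.2 |
|---|---|---|---|---|
| 12 h | 1.00 | 1.04 | 1.13 | 1.40 |
| 24 h | 1.02 | 1.25 | 1.74 | 2.05 |
| 48 h | 1.13 | 1.96 | 1.97 | 1.65 |
| 96 h | 1.73 | 1.81 | 1.34 | 0.93 |

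The bias is mostly upward, but it is negligible in some settings and reverses in the noisiest.

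**The median.** In blood it stays at 0.88 to 1.00 of the true median for half-lives up to 48 h and σ up to 0.8. Under heavier noise it falls, to 0.41 in blood and 0.37 in rectal samples, because the absolute value turns steep rises into short half-lives.

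**The remedy on the same basis.** With a shared half-life and σ = 0.5, log(2) divided by the mean signed rate gives 48 h (5th to 95th percentile 37.5 to 67 h) for blood at a true 48 h. Signed rectal slopes weighted by d² give 24 h (20 to 30 h) at a true 24 h.

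**The case against.** The best defence is that the declining model is stated first, so the absolute value is ordinary shorthand for dropping a minus sign, and only an exception rule is missing. That is fair as to intent. The sentence is still the operative instruction, and followed literally it gives a wrong result whenever a slope is positive.

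Several stronger readings are not supported:

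- **One rising occasion is enough.** A reader might take 10, 8, 12 at 24, 48, 72 h (slope +0.0038/h) as a profile the plan would report with a half-life of 182 h. The plan fits both dosing periods together. If the other period fell with a 48 h half-life (slope −0.0144/h), the common slope would be (0.0038 − 0.0144)/2 = −0.0053/h, with no sign problem and a half-life of about 130 h.
- **Every reported half-life is inflated.** The upward distortion applies to the arithmetic mean and its interval. The median is also planned and is not inflated.
- **The t-interval causes the inflation.** It does not. Its faults are a poor fit to a skewed quantity, negative lower limits, and coverage of 66 to 92% in the noisiest settings. Elsewhere coverage is mostly 94 to 96%.
- **The problem is fully hidden.** Section 8.2.1 plans individual concentration plots and section 5 a range, so rising profiles and extreme half-lives would partly show. The half-life table would still include them.
- **The mean is about doubled.** That is one setting (blood, 48 h, σ = 0.5). At 12 h the effect is negligible and at 24 h modest.

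**Conclusion.** The concern holds in limited form. By the SAP's own model β is minus the slope. The absolute-value rule gives a participant with a positive common slope an apparently valid half-life, no section flags or excludes that case, and a zero slope has no rule. This part is algebra.

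The second part depends on assumptions. The arithmetic mean of log(2)/|slope| and its t-interval can be distorted, usually upward, by near-zero slopes. With σ = 0.5 in blood the typical mean ranges from about 12.4 h for a true 12 h to about 98 h for a true 48 h. The documents give neither σ nor the half-life, so they do not show that this trial's mean will be badly biased, only that the plan leaves it exposed.

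Severity is moderate. The listed primary pharmacokinetic endpoint is concentrations (section 2.2). Half-life is a derived, descriptive summary with no planned test, and no safety conclusion depends on it.

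**What to change.** Amend section 8.2.2 as follows, before half-lives are calculated.

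1. Define β = −slope.
2. In individual listings, show half-life as not estimable when β ≤ 0, and report how many there are per matrix. Count separately the profiles lying entirely at half the LLOQ, and say whether they enter the summary, since their zero slope comes from the substitution.
3. Keep the signed slopes, including non-positive β, in the summary. Dropping them would bias mean β upward.
4. Estimate mean β on the rate scale, by a pooled or mixed model or by signed slopes weighted by the sampling-time design. Do not weight by each participant's own fitted standard error, which rests on 3 (blood) or 1 (rectal) residual degrees of freedom.
5. Report log(2)/(mean β), with limits transformed from the confidence interval for β. State the upper limit as unbounded if that interval includes zero.
6. Also show the median of the individual half-lives.

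The cost is SAP wording and a few lines of code, with no new data. Some individual half-lives will be listed as not estimable. Also, log(2)/(mean β) is a harmonic-type average, about 0.96 of the true median at the assumed 30% CV, and should be labelled as such. A geometric mean of log(2)/|slope| would reduce the inflation but would not resolve the sign problem.
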